### **3.1.6 Post-Treatment Follow-Up and Survival Follow-Up**

Patients who complete treatment or discontinue treatment for reasons other than disease progression will undergo assessments every 3 months during the post-treatment follow-up period, which will continue until disease progression, the start of new anti-lymphoma treatment, or the end of the study (as defined below), whichever occurs first. Patients who experience disease progression will be evaluated for survival status and initiation of new anti-lymphoma treatment every 3 months until the end of the study. Details are provided in the schedules of activities (see [Appendix 1](#) and [Appendix 2](#)).

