**Table 15 Idasanutlin Dose-Reduction Steps**

Initial Dose	Dose Reduction in Milligrams		
	Step 1	Step 2	Step 3
100 mg	Minus 50 mg	No further reduction a	No further reduction a
150 mg	Minus 50 mg	No further reduction a	No further reduction a
200 mg	Minus 50 mg	Minus 50 mg	No further reduction a
250 mg	Minus 100 mg	Minus 50 mg	No further reduction a
300 mg	Minus 100 mg	Minus 50 mg	Minus 50 mg
350 mg	Minus 100 mg	Minus 100 mg	Minus 50 mg
400 mg	Minus 100 mg	Minus 100 mg	Minus 50 mg

a When no further idasanutlin dose reduction is possible, the patient will be discontinued from the study.

The dose of venetoclax will be reduced by at least 25% from the current dose (rounded to the lower closest 50 mg) or return to the previous dose, with a minimum final dose of 200 mg. If the dose level reaches 200 mg, no further reduction will be allowed and the patient will be discontinued from the study.

Toxicities that occur during the cycle and subside prior to the next cycle should not trigger the suggested dose modifications. Guidelines for management of toxicities during induction treatment are provided in Section 5.1.8.1 and during consolidation or maintenance treatment in Section 5.1.8.2.

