Grade 3 or 4 hematologic toxicity a, b	
For patients who have had one or no prior dose reductions:
 
 
• Withhold study treatment.a
 
• Administer RBCs or platelets as required.
 
• If patient has not already initiated G-CSF, initiate prophylactic G-CSF for current and subsequent cycles.
 
• If improvement to Grade <math>\leq 2</math> or baseline within <math>\leq 14</math> days after the scheduled date for the next cycle, resume obinutuzumab or rituximab at full dose and resume idasanutlin and venetoclax at current dose.
 
• If improvement to Grade <math>\leq 2</math> or baseline 15–21 days after the scheduled date for the next cycle, resume obinutuzumab or rituximab at the full dose and resume the last escalated drug(s) at a reduced dose according to guidelines in Section 5.1.8.1 for current and subsequent cycles.
 
 
No more than three dose reductions of idasanutlin or venetoclax are allowed.
 
 
• If study treatment is withheld for <math>>21</math> days, permanently discontinue study treatment.
 
• Permanently discontinue study treatment if any of the following events occur: 
 
– Grade 3 or 4 thrombocytopenia of any duration if associated with Grade <math>\geq 3</math> bleeding
 
– Recurrent Grade 3 or 4 neutropenia if associated with fever of <math>>38^{\circ}\text{C}</math> for <math>>5</math> days) or a documented infection despite use of G-CSF and after one idasanutlin dose reduction and/or one venetoclax dose reduction or reduced schedule
 
– Recurrent Grade 4 neutropenia or thrombocytopenia lasting more than 7 days despite use of G-CSF (for neutropenia) and after one idasanutlin dose reduction and/or one venetoclax dose reduction/reduced schedule
 
 
 
 
For patients who present with recurrent Grade 3 thrombocytopenia/neutropenia in consecutive cycles:
 
If despite the use of G-CSF, for subsequent cycles, modify the venetoclax dose by reducing to next dose level or decrease the dosing schedule; reduce idasanutlin to the next dose level (see guidelines in Section 5.1.8.1).
 
For patients who have had reductions in three doses (either as single drug dose reduction or double drug reduction in the same time) or for patients who reach the lowest dose level and no further dose reduction is applicable (see Section 5.1.8):
 
 
• Permanently discontinue study treatment.
 

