**Table 18 Guidelines for Management of Non-Hematologic Toxicities (cont.)**

Event	Action to Be Taken
Nausea and vomiting	
Grade 4 vomiting:
 
 
• Permanently discontinue study treatment.
 
 
Grade 1, 2, or 3 vomiting or nausea:
 
 
• Consider prophylaxis with second-generation anti-emetics like palonosetron, ondansetron, or granisetron.
 
• If vomiting occurs within 15 minutes of taking idasanutlin and/or venetoclax, and all expelled tablets are still intact, another dose may be given and the second dose noted in the drug log. Otherwise, no replacement dose is to be given (see Sections 5.1.8.1 and 5.1.8.2).
 

Dermatologic toxicity	Permanently discontinue rituximab in the event of Stevens-Johnson syndrome or toxic epidermal necrolysis.

Other non-hematologic toxicities (i.e., not described above), excluding alopecia
 
Grade 3 or 4
 
Grade 2
	
Grade 4 events
 
 
• Permanently discontinue study treatment.
 
 
Grade 3 events
 
 
• Withhold study treatment.a
 
 
If improvement to Grade <math>\leq 1</math> or baseline, resume obinutuzumab or rituximab at the full dose and resume idasanutlin and venetoclax at reduced (Section 5.1.8) dosea for subsequent cycles. No more than three dose reductions of idasanutlin or venetoclax are allowed.
 
For patients who have had three prior dose reductions (either as a single drug dose reduction or double drug reduction in the same time) or for patients who reach the lowest dose level and no further dose reduction is applicable (See Section 5.1.8):
 
 
• Permanently discontinue study treatment.
 
 <hr/> 
 
• Withhold study treatment.a, b
 
• If improvement to Grade <math>\leq 1</math> or baseline, resume obinutuzumab or rituximab at the full dose and resume idasanutlin and venetoclax at the current dose.
 

IRR=infusion-related reaction; PML=progressive multifocal leukoencephalopathy; ULN=upper limit normal.

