- e Patients who complete treatment or discontinue treatment for reasons other than disease progression will undergo assessments every 3 months during the post-treatment FU period, which will continue until disease progression, the start of new anti-lymphoma treatment, or the end of the study, whichever occurs first. The first post-treatment FU visit is 3 months after the EOI visit for patients who do not receive maintenance treatment and 3 months after the last dose for patients who receive maintenance treatment. Patients who experience disease progression or start another anti-lymphoma treatment will be evaluated for survival status and new anti-lymphoma treatment every 3 months during the survival follow-up period, which will continue until the end of the study. The end of the study is defined as the time when all enrolled FL patients have completed or discontinued study treatment and all enrolled DLBCL patients have been followed for at least 1 year after they have completed or discontinued study treatment.
- f Informed consent must be documented before any study-specific screening procedure is performed.
- g Vital signs include respiratory rate, pulse rate, body temperature, and systolic and diastolic blood pressures while the patient is in a seated position. For obinutuzumab infusions: For the first cycle and for patients who experience an infusion-related reaction, vital signs will be measured prior to the infusion, every 15 ( $\pm$ 5) minutes for the first 90 minutes of the infusion, and then every 30 ( $\pm$ 10) minutes until 1 hour after completion of the infusion. For the second and subsequent cycles, vital signs will be measured every 30 minutes during the infusion, except for patients who have experienced an infusion-related reaction during a prior infusion. For venetoclax, serial vital signs will be measured and TLS laboratory samples will be drawn (serum chemistry as defined in Section 4.5.6) prior to the first dose of venetoclax and 8, 12, and 24 hour post-dose.
- h Perform only for patients who will not be receiving maintenance treatment.

## Appendix 1

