### Schedule of Activities for Patients with Follicular Lymphoma: Dose-Escalation and Expansion Phases (cont.)

---

- x Refer to [Appendix 3](#) for detailed schedule.
- y Includes circulating lymphoma cells and/or cell-free circulating-tumor DNA.
- z Includes B-cell counts (CD19), T-cell counts (CD3, CD4, and CD8), and natural killer cell counts (CD16 and CD56).
- aa Requires separate patient consent for RBR participation. Not applicable for a site that has not been granted approval for RBR sampling.
- bb Availability of adequate archival or freshly biopsied tumor tissue samples should be confirmed at screening (see Section [4.5.6](#) for details).
- cc A tumor biopsy sample is preferred and recommended at the time of progression unless no adequate tumor site is accessible.
- dd After informed consent has been obtained but prior to initiation of study treatment, only serious adverse events caused by a protocol-mandated intervention should be reported. After initiation of study treatment, all adverse events will be reported until 90 days after the last dose of study treatment. After this period, the Sponsor should be notified if the investigator becomes aware of any serious adverse event that is believed to be related to prior study treatment (see Section [5.6](#)). An exception is made for Grade 3 and 4 infections (related and unrelated) in patients who received obinutuzumab, which should be reported until up to 2 years after the last dose of study treatment. The investigator should follow each adverse event until the event has resolved to baseline grade or better, the event is assessed as stable by the investigator, the patient is lost to follow-up, or the patient withdraws consent. Every effort should be made to follow all serious adverse events considered to be related to any of the study treatment components or trial-related procedures until a final outcome can be reported.
- ee The screening PET-CT scan must be performed within 35 days prior to Day 1 of Cycle 1.
- ff Perform only for patients who receive at least two cycles of induction treatment.
- gg If PET-CT scan is positive at the EOI, perform 12 months after initiation of induction treatment, within 14 days prior to study treatment administration.

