### Schedule of Activities for Patients with Diffuse Large B-Cell Lymphoma: Dose-Escalation and Expansion Phases (cont.)

- x Perform every 3 months until recovery to either normal range or baseline level, disease progression, or the start of new anti-lymphoma treatment, whichever occurs first.
- y Refer to [Appendix 3](#) for detailed schedule.
- z Includes circulating lymphoma cells and/or cell-free circulating-tumor DNA.
- aa Includes B-cell counts (CD19), T-cell counts (CD3, CD4, and CD8), and natural killer cell counts (CD16 and CD56).
- bb Requires separate patient consent for RBR participation. Not applicable for a site that has not been granted approval for RBR sampling.
- cc Availability of adequate archival or freshly biopsied tumor tissue samples should be confirmed at screening (see Section [4.5.6](#) for details).
- dd A tumor biopsy sample is preferred and recommended at the time of progression unless no adequate tumor site is accessible.
- ee After informed consent has been obtained but prior to initiation of study treatment, only serious adverse events caused by a protocol-mandated intervention should be reported. After initiation of study treatment, all adverse events will be reported until 90 days after the last dose of study treatment. After this period, the Sponsor should be notified if the investigator becomes aware of any serious adverse event that is believed to be related to prior study treatment (see Section [5.6](#)). An exception is made for Grade 3 and 4 infections (related and unrelated) in patients who received obinutuzumab, which should be reported until up to 2 years after the last dose of obinutuzumab. The investigator should follow each adverse event until the event has resolved to baseline grade or better, the event is assessed as stable by the investigator, the patient is lost to follow-up, or the patient withdraws consent. Every effort should be made to follow all serious adverse events considered to be related to any of the study treatment components or trial-related procedures until a final outcome can be reported.
- ff The screening PET-CT scan must be performed within 35 days prior to Day 1 of Cycle 1.
- gg Perform only for patients who have received at least two cycles of induction treatment.

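### At the dose floor, Section 5.1.8 takes the patient off the study, while the toxicity tables and follow-up sections stop study treatment only

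*Protocol*

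**What the plan says.** Section 5.1.8 of the protocol sets a floor for each oral drug and says what happens there.

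- Venetoclax, minimum 200 mg: "If the dose level reaches 200 mg, no further reduction will be allowed and the patient will be discontinued from the study".
- Idasanutlin, Table 15 footnote a: "When no further idasanutlin dose reduction is possible, the patient will be discontinued from the study".

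The management tables in Section 5.1.8.1 cover the same situation. Table 16 (hematologic toxicity) has an entry "for patients who reach the lowest dose level and no further dose reduction is applicable (see Section 5.1.8"), and Table 18 repeats it for other non-hematologic toxicity. In both, the action is permanent discontinuation of study treatment, not of study participation.

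Section 3.1.6 provides that patients who complete or "discontinue treatment for reasons other than disease progression will undergo assessments every 3 months" until progression, new anti-lymphoma therapy or the end of the study. Appendix 1 footnote e adds: "The first post-treatment FU visit is 3 months after the EOI visit for patients who do not receive maintenance treatment". Footnote c of Appendices 1 and 2 gives patients who stop induction early for an adverse event their own window for end-of-induction (EOI) assessments, 4 to 8 weeks after the last dose. EOI imaging carries one condition, in Appendix 1 footnote ff: "Perform only for patients who receive at least two cycles of induction treatment". Appendix 2 footnote gg sets the same condition.

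**The concern.** One clinical event carries two instructions, and they have different consequences for data collection. Under the tables, the patient stops the drugs and continues to the EOI visit and 3-monthly follow-up. Under Section 5.1.8 as written, the patient leaves the study.

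The primary efficacy endpoint is complete response (CR) at EOI by independent review of PET-CT. PFS, EFS and OS depend on follow-up after treatment. If some sites act on the Section 5.1.8 wording, these data go missing in one kind of patient only: those who exhausted the dose reductions because of toxicity. Sites could also differ in which rule they apply.

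The non-responder rule in Section 6.5.1 of the protocol and Section 5.1 of the SAP does not fully close the gap. It covers patients with no post-baseline tumor assessment. A CT is scheduled shortly before Day 1 of Cycle 3, so a patient removed after that scan has a post-baseline assessment but no EOI result, and the stated rule does not reach that case.

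**Working it through.** The main check is a comparison of texts.

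1. **Same trigger?** Yes. Section 5.1.8 and Table 15 footnote a apply when no further reduction is possible. Tables 16 and 18 apply at the lowest dose level with no further reduction available, and both point to Section 5.1.8. The table entries sit in the rows for Grade 3 or 4 hematologic toxicity and for other non-hematologic toxicity, while Section 5.1.8 speaks generally. Within those rows the two instructions overlap fully.

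2. **Same action?** No. Section 5.1.8 ends study participation; the tables end study treatment. Section 5.1.8 itself uses treatment wording elsewhere, for delays beyond 21 days.

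3. **Do the documents treat these as different events?** Yes.
   - Section 4.6.1 covers leaving the study. Its list of reasons is not exhaustive and does not name the dose floor.
   - Section 4.6.2 covers stopping treatment. It places there the hematologic events that meet the Section 5.1.8 criteria for permanent discontinuation.
   - Section 6.2 reports study discontinuations and treatment discontinuations separately.
   - SAP Output 2 puts a patient who has stopped all drugs in follow-up, or among study discontinuations if a study discontinuation is recorded.
   - SAP Section 2.3.4.5 ends survival follow-up at the date on the study completion or early discontinuation page.

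4. **What would be lost under the literal reading?** The EOI PET-CT if treatment stops during induction after at least two cycles, and the 3-monthly assessments. By Section 6.5.3, PFS and EFS would then be censored at the last tumor assessment and OS at the date last known alive. Adverse event reporting to 90 days after the last dose is a separate rule and does not change.

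5. **Bound for one lost patient.** The documents give no figure for this point. Section 6.1.2 assumes an observed CR rate of 55% in 40 patients, that is 0.55 × 40 = 22, and seeks to rule out 40%. Table 21 prints a 90% Clopper-Pearson interval of 0.40 to 0.68; the exact limits for 22/40 are 0.4088 and 0.6854. If one of these patients is lost:
   - Counted as a non-responder: 21/40 (lower limit 38.5%) if the patient would have been a CR, otherwise unchanged at 22/40 (40.9%). The change in the rate is between 0 and 1/40 = 2.5 percentage points.
   - Excluded from the denominator: 21/39 (lower limit 39.6%) if the patient would have been a CR, otherwise 22/39 (42.1%).

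   These figures bound one patient. They say nothing about how many patients would be lost, and they would apply to any missing EOI scan.

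**The case against.** The strongest reply is that the intended meaning can be recovered. Section 4.6.2 files the Section 5.1.8 hematologic criteria under treatment discontinuation, Tables 16 and 18 agree, and footnote c foresees EOI assessments after an adverse-event stop. Many sites would read Section 5.1.8 in that light. Nor does leaving the study automatically end all data collection: Section 4.6.1 asks for efforts to obtain information on withdrawn patients and bars follow-up only after consent is withdrawn. PFS, EFS and OS are exploratory and descriptive.

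Most of this stands. It makes the data loss possible rather than certain, and it makes the problem one of wording rather than design. It does not remove the conflict, because Section 5.1.8 is the text the tables send the reader to and it states the opposite outcome twice.

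Three stronger readings are tempting and are not supported.

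- **Being at 200 mg is enough for removal.** Taken in isolation, the venetoclax sentence could be read that way. But 200 mg is both the permitted minimum and the escalation starting dose, so whole cohorts would leave at the first dose. Section 5.1.8 also limits dose modifications to toxicities related to idasanutlin or venetoclax.
- **The 50% venetoclax cut for a moderate CYP3A inhibitor triggers removal.** Table 9 footnote b describes an interaction adjustment that is later reversed, whereas reductions under Section 5.1.8 may not be re-escalated. They are different mechanisms.
- **The number of cycles before a floor stop can be read from the reduction steps.** In dose escalation, an adverse event in Cycles 1 or 2 that delays the next cycle by more than 14 days is a DLT and ends treatment (Sections 3.1.2 and 3.1.2.1), while the hematologic reduction in Table 16 needs recovery at 15 to 21 days. Grade 3 diarrhea on Days 1 to 5 can instead reduce the dose within the current cycle (Table 18). Whether a given patient meets the two-cycle imaging condition therefore cannot be fixed in advance.

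**Conclusion.** The point holds as a conflict between operative instructions. Section 5.1.8 and Table 15 footnote a are wrong as written when set against Tables 16 and 18, Section 4.6.2, Section 3.1.6 and footnote c. Treatment discontinuation is probably what the sponsor intends.

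The consequence depends on sites acting on the literal words. If they do, EOI imaging and later follow-up could be lost selectively in patients stopped for toxicity. The frequency is unknown, and the effect on the CR rate may be nil. The one-patient bound of 0 to 2.5 percentage points assumes 40 patients in the cohort and that the lost patient is counted as a non-responder. A reader might infer a known bias in the primary result; the documents do not support that. The correction is worth making because it protects ascertainment of the primary endpoint at almost no cost.

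**What to change.** Replace the outcome in both places in Section 5.1.8 (the venetoclax sentence and Table 15 footnote a) with wording such as:

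*If a further toxicity-related reduction is required and none is possible, the patient is permanently discontinued from study treatment, subject to Section 4.6.2. The patient remains in the study, has the EOI assessments in Appendix 1 or 2 (footnote c and the two-cycle imaging condition) if treatment stops during induction, and is followed according to Section 3.1.6.*

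In Table 19, which now says only that such patients are permanently discontinued, add that this means from study treatment. That change is for consistency.

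The 200 mg minimum, the reduction steps and footnote c stay as they are. The cost is an amendment to wording in three places. No visit or scan is added, since the EOI visit and 3-monthly follow-up are already scheduled.

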### **5.1.8.1 Toxicities during Induction Treatment Hematologic Toxicities during Induction Treatment**

Guidelines for management of hematologic toxicities that occur during induction treatment, with the exception on Days 8 and 15 of Cycle 1 when obinutuzumab are given in Table 16. Hematologic toxicity is defined as neutropenia, anemia, or thrombocytopenia. Lymphopenia is not considered a hematologic toxicity but an expected outcome of therapy.

**Table 16 Guidelines for Management of Hematologic Toxicities That Occur during Induction Treatment (Except on Days 8 and 15 of Cycle 1)**

Event	Action to Be Taken
Grade 3 or 4 hematologic toxicity a, b	
For patients who have had one or no prior dose reductions:
 
 
• Withhold study treatment.a
 
• Administer RBCs or platelets as required.
 
• If patient has not already initiated G-CSF, initiate prophylactic G-CSF for current and subsequent cycles.
 
• If improvement to Grade <math>\leq 2</math> or baseline within <math>\leq 14</math> days after the scheduled date for the next cycle, resume obinutuzumab or rituximab at full dose and resume idasanutlin and venetoclax at current dose.
 
• If improvement to Grade <math>\leq 2</math> or baseline 15–21 days after the scheduled date for the next cycle, resume obinutuzumab or rituximab at the full dose and resume the last escalated drug(s) at a reduced dose according to guidelines in Section 5.1.8.1 for current and subsequent cycles.
 
 
No more than three dose reductions of idasanutlin or venetoclax are allowed.
 
 
• If study treatment is withheld for <math>>21</math> days, permanently discontinue study treatment.
 
• Permanently discontinue study treatment if any of the following events occur: 
 
– Grade 3 or 4 thrombocytopenia of any duration if associated with Grade <math>\geq 3</math> bleeding
 
– Recurrent Grade 3 or 4 neutropenia if associated with fever of <math>>38^{\circ}\text{C}</math> for <math>>5</math> days) or a documented infection despite use of G-CSF and after one idasanutlin dose reduction and/or one venetoclax dose reduction or reduced schedule
 
– Recurrent Grade 4 neutropenia or thrombocytopenia lasting more than 7 days despite use of G-CSF (for neutropenia) and after one idasanutlin dose reduction and/or one venetoclax dose reduction/reduced schedule
 
 
 
 
For patients who present with recurrent Grade 3 thrombocytopenia/neutropenia in consecutive cycles:
 
If despite the use of G-CSF, for subsequent cycles, modify the venetoclax dose by reducing to next dose level or decrease the dosing schedule; reduce idasanutlin to the next dose level (see guidelines in Section 5.1.8.1).
 
For patients who have had reductions in three doses (either as single drug dose reduction or double drug reduction in the same time) or for patients who reach the lowest dose level and no further dose reduction is applicable (see Section 5.1.8):
 
 
• Permanently discontinue study treatment.
 


G-CSF = granulocyte colony-stimulating factor.

a Treatment delays apply to all toxicities; dose modifications apply only to toxicities that are considered to be related to any of the study treatment components.

b If cytopenia is thought to be caused mainly by B-cell lymphoma infiltration of the bone marrow, the investigator may decide not to reduce idasanutlin or venetoclax doses.

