### 3.1.2.1 Definition of Dose-Limiting Toxicity

In this study, a DLT is defined as at least one of the following events occurring during the first two cycles of treatment and assessed by the investigator as clearly not related to the patient's underlying disease:

- Any Grade 5 adverse event unless unequivocally due to the underlying malignancy or extraneous causes
- Adverse event of any grade that leads to a delay of more than 14 days in the start of the next treatment cycle
- Hematologic adverse events that meet any of the following criteria:
  - Grade 3 or 4 neutropenia in the presence of sustained fever of  $>38^{\circ}\text{C}$  (lasting for  $>5$  days) or a documented infection
  - Grade 4 neutropenia lasting for  $>7$  days *despite adequate supportive care measures. G-CSF may be used to treat Grade  $\geq 3$  neutropenia but should not be used as prophylaxis in the DLT period.*
  - Grade 3 or 4 thrombocytopenia if associated with grade  $\geq 3$  bleeding
  - Grade 4 thrombocytopenia lasting for  $>7$  days
- Grade 3 or 4 non-hematologic adverse event, with the following exceptions:
  - Grade 3 or 4 IRRs
    - Note that IRRs are not dose-dependent events. They may occur even after a small amount of drug has been administered.
  - Grade 3 laboratory TLS without manifestations of clinical TLS (see [Appendix 5](#) for the Howard-based criteria for clinical and laboratory TLS)
  - Grade 3 AST or ALT increase lasting  $<7$  days
  - Grade 3 diarrhea that responds to adequate therapy within 48 hours

- Grade 3 nausea or vomiting that occurs in the absence of premedication and responds to adequate therapy within 72 hours
- Grade  $\leq 3$  fatigue, asthenia, anorexia, or constipation that resolves to Grade  $\leq 2$  in  $\leq 7$  days
- Any increase in hepatic transaminase  $> 3 \times$  baseline AND an increase in direct bilirubin  $> 2 \times$  ULN, WITHOUT any findings of cholestasis or jaundice or signs of hepatic dysfunction AND in the absence of other contributory factors (e.g., worsening of metastatic disease or concomitant exposure to known hepatotoxic agent or of a documented infectious etiology) is suggestive of potential drug induced liver injury (DILI) (according to Hy's Law) and will be considered a DLT.

Other toxicities that are considered clinically relevant and related to study treatment as determined by the investigator and the Medical Monitor may also be considered DLTs.

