### **4.4.1 Permitted Therapy**

Premedication is permitted as described in Section [4.3.2.5](#).

Patients who use oral contraceptives, hormone-replacement therapy, or other maintenance therapy should continue their use.

Hematopoietic growth factors are allowed in *all study phases* if clinically indicated and used in accordance with the prescribing information. *G-CSF may be used in the DLT period (Cycles 1 and 2) to treat Grade  $\geq 3$  neutropenia, but is not allowed as prophylaxis. Outside of the DLT observation window during the dose-escalation phase and during the expansion phase, G-CSF may be administered in each cycle of therapy*

as primary prophylaxis for neutropenia, according to the American Society of Clinical Oncology (ASCO), EORTC, and European Society for Medical Oncology (ESMO) guidelines ([Smith et al. 2006](#)) or according to each site's institutional standards.

Prophylactic treatment with antibiotics should be administered as per standard practice.

Necessary supportive measures for optimal medical care will be given throughout the study according to institutional standards.

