Severe thrombocytopenia a or symptomatic bleeding (irrespective of platelet count)	
 
• Withhold obinutuzumab and venetoclax until platelet count is <math>\geq 50,000</math> cells/<math>\mu\text{L}</math> with resolution of bleeding and resume at the next scheduled dose.
 
• Consider prophylactic or therapeutic platelet transfusion as appropriate
 
• In patients with HLA sensitization, HLA-compatible platelet transfusions should be administered.
 
• If the dose on Day 8 of Cycle 1 is delayed by <math>\leq 2</math> days, Day 15 of Cycle 1 should be delayed by the same number of days to retain the treatment interval for obinutuzumab.
 
• If the dose on Day 8 of Cycle 1 dose is delayed by <math>> 2</math> days, omit the Day 8 dose and administer the Day 15 dose as previously scheduled (if severe thrombocytopenia and/or symptomatic bleeding have resolved).
 
• If the dose on Day 15 of Cycle 1 is delayed by <math>> 2</math> days, omit the Day 15 dose and administer the next dose (Day 1 of Cycle 2) of obinutuzumab, venetoclax, and idasanutlin as scheduled (if severe thrombocytopenia and/or symptomatic bleeding have resolved).
 
• If the event is ongoing at Day 1 of Cycle 2, follow instructions in Table 18.
 

G-CSF = *granulocyte colony-stimulating factor*; HLA = human leukocyte antigen; QD = once a day.

a Severe thrombocytopenia is defined as a platelet count  $< 10,000$  cells/ $\mu\text{L}$  for patients who are not receiving concomitant anticoagulants or platelet inhibitors and  $< 20,000$  cells/ $\mu\text{L}$  for patients who are receiving concomitant aspirin.

b In the dose-escalation phase, prophylactic G-CSF should start after Cycle 2.

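### Table 16 orders prophylactic G-CSF without the dose-escalation exception, so it conflicts with the ban on prophylaxis in Cycles 1 and 2

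*Protocol*

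**What the plan says.** Table 16 (protocol Section 5.1.8.1) covers hematologic toxicity throughout induction except on Days 8 and 15 of Cycle 1. For a Grade 3 or 4 event it withholds treatment and adds: "If patient has not already initiated G-CSF, initiate prophylactic G-CSF for current and subsequent cycles". If recovery comes within 14 days of the scheduled start of the next cycle, the site is to "resume obinutuzumab or rituximab at full dose and resume idasanutlin and venetoclax at current dose". The table has two footnotes. One concerns treatment delays and dose modifications. The other begins "If cytopenia is thought to be caused mainly by B-cell lymphoma infiltration of the bone marrow" and concerns dose reduction.

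The DLT definition in Section 3.1.2.1 permits G-CSF to treat Grade 3 or higher neutropenia but says that it "should not be used as prophylaxis in the DLT period". Section 4.4.1 identifies that period as Cycles 1 and 2 and says of G-CSF that it may treat such neutropenia "but is not allowed as prophylaxis".

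Table 17, for events on Days 8 and 15 of Cycle 1, has nearly the same G-CSF bullet, with a footnote: "In the dose-escalation phase, prophylactic G-CSF should start after Cycle 2".

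**The concern.** Two operative instructions apply to the same patient in the same cycle and cannot both be followed. A site working from the toxicity table would give prophylaxis that the DLT definition forbids.

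This matters because the neutropenic DLT criteria depend on duration, sustained fever or infection, which are the outcomes that prophylaxis is meant to reduce. The DLT counts feed the modified continual reassessment model in Section 3.1.2.3, with its 16%–33% target interval and its limit of 35% on the probability that the DLT rate exceeds 33%. Any loss of Cycle 2 DLTs would make a dose look better tolerated than it is and so favor escalation. If sites resolve the conflict differently, DLT data from different patients at one dose would also be collected under different supportive care.

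**Working it through.** The plan gives no figure to reproduce and no rate can be computed. The check is whether a patient can reach the conflict under the protocol's own thresholds.

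1. **When the table applies.** Section 5.1.8 bases the toxicity guidelines on laboratory values from the 48 hours before Day 1 of each scheduled administration, or the 24 hours before Days 8 and 15 of Cycle 1. Days 8 and 15 of Cycle 1 belong to Table 17 for patients on obinutuzumab. The main scheduled trigger for Table 16 inside the DLT window is therefore the check before Cycle 2 Day 1.

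2. **Is the event a DLT?** Under Section 3.1.2.1, Grade 3 neutropenia without sustained fever or documented infection is not a DLT. Nor is Grade 4 neutropenia lasting 7 days or less without those complications. A patient with such an event at the pre-Cycle 2 check stays on study; a patient with a DLT discontinues (Section 3.1.2).

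3. **What the delay does.** The delay criterion is "Adverse event of any grade that leads to a delay of more than 14 days in the start of the next treatment cycle".
   - Recovery within 14 days: not a DLT. Table 16 resumes all drugs at the current dose, with prophylactic G-CSF already ordered for the cycles that follow. Cycle 2 then runs under prophylaxis. **Conflict.**
   - Recovery at 15–21 days: the delayed Cycle 2 is itself a DLT and treatment ends. No conflict.

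4. **Which part is the conflict.** G-CSF given while neutropenia is Grade 3 or higher is permitted treatment. The conflict begins when it continues after recovery to Grade 2 or better, within Cycle 2.

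5. **Neutropenia arising later in Cycle 2.** The next cycle is Cycle 3, where prophylaxis is allowed. Carry-over raises no conflict.

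6. **Cytopenia in Cycle 1 that resolves before the check.** Unclear. The Table 16 bullet has no such limit, but the laboratory rule in Section 5.1.8 points to the pre-Day 1 value, and that section also says that toxicities which have subsided by the next cycle do not trigger dose modification. It does not say whether the same holds for starting G-CSF.

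7. **Section 5.1.5.2.** One sentence starts primary prophylaxis at Cycle 3 in dose escalation, yet also makes it mandatory after a first Grade 3 or higher neutropenia in the study treatment period, citing Section 5.1.8, where Table 16 sits. It can be read either way for Cycle 2.

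8. **Which toxicity triggers the bullet.** Section 5.1.8.1 defines hematologic toxicity as neutropenia, anemia or thrombocytopenia, so read literally all three lead to G-CSF. The same row later ties G-CSF to neutropenia ("lasting more than 7 days despite use of G-CSF (for neutropenia"), so neutropenia is probably what was meant.

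**The case against.** The best defense is that the specific rule governs. Sections 3.1.2.1 and 4.4.1 state the ban outright, Table 17 repeats it, and Sections 5.1.1.3 and 5.1.3.2 send readers to Section 4.4.1. Table 16 is a general guideline for both phases and all six cycles. Since a patient who is neutropenic at the pre-Cycle 2 check may receive G-CSF as treatment anyway, the extra exposure is only what continues after recovery. Clinical judgment also overrides the model.

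Much of this stands, and it is why the effect is probably small. It does not remove the conflict. No clause says which text prevails; if the general sections were enough, Table 17 would not need its footnote. Section 5.1.5.2 also sends the reader back toward Table 16. Calling the use secondary prophylaxis does not help, because the ban is not confined to primary prophylaxis.

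A reader might infer three stronger things, none of which the documents support:

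- **That any Grade 3 or 4 cytopenia in Cycle 1 brings prohibited prophylaxis into Cycle 2.** Step 6 shows that this is unsettled once an event has resolved before the pre-Cycle 2 check.
- **That Regimen B is hit hardest, because Cycle 2 is its only combination cycle in the window.** There the trigger at the pre-Cycle 2 check would have to come from obinutuzumab alone. Table 13 lists Grade 3 or higher neutropenia on monotherapy at 5%–14% for obinutuzumab, against 24% for idasanutlin and 13% for venetoclax. These are not Cycle 1 rates, but they give no ground for ranking Regimen B first.
- **That the rituximab bridging cohorts are hit hardest, because they have no Day 8 or 15 infusion and so fall outside Table 17.** Wider reach of Table 16 does not show that its trigger is more frequent; Section 3.3.2.1 expects less overlapping toxicity with rituximab.

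**Conclusion.** The inconsistency is real and should be fixed. It is certain for one path: a dose-escalation patient with non-DLT Grade 3 or 4 neutropenia at the pre-Cycle 2 Day 1 check who recovers within 14 days. For cytopenia that resolves before that check, the text is ambiguous. This is an internal inconsistency, not a questionable design choice, since the intended rule is clear from Sections 3.1.2.1 and 4.4.1 and Table 17.

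The direction of any effect is toward fewer recorded neutropenic DLTs in Cycle 2. That assumes sites follow Table 16 literally and that prophylaxis prevents events which treatment alone would not. The documents give neither the frequency of the path nor the size of that benefit, so the effect is unquantified. A reader might conclude that the dose recommendation would be materially biased; nothing in the documents establishes that.

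**What to change.** - Attach Table 17's dose-escalation footnote to the G-CSF bullet in Table 16.
- Limit that bullet to neutropenia, and state there that in Cycles 1 and 2 of dose escalation G-CSF is only for treating Grade 3 or higher neutropenia.
- Add the same limit to the clause in Section 5.1.5.2 that makes prophylaxis mandatory after a first event. Amending Table 16 alone would leave that route open.
- As a separate editorial item, Table 17 sends events still ongoing at Cycle 2 Day 1 to Table 18, which covers non-hematologic toxicity; it should point to Table 16. Make this change at the same time: corrected alone, it would direct more patients to the unqualified instruction.

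The cost is one footnote, wording limits in two places and one cross-reference. Design, data collection and analysis are unaffected.
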